5. TREATMENT OF SUBJECTS

5.1 Investigational product/treatment

Participants will be informed that IFL is the standard treatment. However they can opt for an alternative treatment: the SLN procedure. They will be informed that it is not known yet if this SLN procedure is as safe as IFL, however that short and long time sequels like lymph oedema and recurrent erysipelas are less frequent in the SLN group based on data of primary vulvar SCC. The surgical SLN procedure will be performed as per protocol. The SLNs are removed and sent separately for pathologic examination (including ultra-staging with immunohistochemistry).

5.1.1 Preoperative assessment

In accordance with current routine pre-operative imaging of the chest, abdomen and inguinal area is done by CT scan. In case of enlarged (> 10mm short axis) or suspicious nodes ultrasound of the groins with FNA should be performed to rule out metastatic involvement. When FNA is negative, patients can proceed to SLN procedure, the gynaecologic oncologist should in these cases be ensured that at least all (suspicious) enlarged nodes are removed.

5.1.2 Preoperative definition of planned surgery

Prior to surgery the gynaecologic oncologist has to state what groin surgery should be done; ipsi or bilateral groin treatment and what treatment should be done in case the SLN is not visible, or not found during surgery. This decision relates to the previous groin treatment and whether or not the tumour crosses the midline. (See figures planned surgery). All SLN shown by imaging should be removed, also contralateral nodes in lateral tumours, and nodes in groins previously treated with IFL or radiotherapy, unless stated otherwise prior to surgery. In the current (standard) treatment protocol (www.oncoline.nl) groin surgery is not performed in local recurrent vulvar cancer after a previous IFL. Women should have an IFL in case of technical problems (SLN does not appear on the scintigraphy, or cannot be retrieved at surgery). Women that do not consent for a full IFL in case of technical problems (SLN does not appear on the scintigraphy, or cannot be retrieved at surgery), are more likely to experience groin recurrences (post-priory 17%). When women do not consent for IFL this should be noted prior to surgery.

Figures flow charts planned surgery see addendum 2.

5.1.3 Sentinel node detection protocol

Three to 24 hours before the surgical procedure, 0.5 ml 30 - 100 MBq (depending on the local protocol, interval between injection and surgery, sensitivity of the probe etc.) ^{99m}Tc-labeled Nano colloid with a particle size < 80 nm is injected circumferentially intradermal on 4 locations around the primary tumour. In accordance with local protocols IGn labelled Nano colloid is used. Half an hour before the injections lidocaine-prilocaine 5% cream will be applied on the vulva for pain relief. Anterior images are obtained using a single head gamma camera with a low energy high resolution collimator. Within 5 minutes after injection dynamic imaging is started within 30 sec frames during 30 minutes. A static image is obtained after 2.5 hours. In order to facilitate interpretation transmission scanning will be done simultaneously using the 120 KeV gamma rays of a ⁵⁷Co flood source. The first appearing persistent focal accumulation is considered to be a sentinel node, especially when a direct connection from the injection site to the sentinel inguinofemoral node is visible. In accordance with local protocols a SPECT CT scan is made to detect the sentinel node.

On the day or the afternoon after the injection of the radioactive tracer, following induction of anaesthesia, ca. 0.5-1.0 ml of the blue dye (e.g. Patent blue-V (2.5% in aqueous solution containing 0.6% sodium chloride and 0.05% disodium hydrogen phosphate) is injected intradermal on the same 4 locations around the primary tumour approximately 5-10 minutes prior to the surgical procedure. The surgical procedure starts with identification and removal of the sentinel nodes. During surgery a handheld gamma-ray-detection probe is used to confirm the area of greatest activity in the groin. A small skin incision is made and a sentinel node excision biopsy is performed using the handheld gamma-ray detector and by dissection of blue-stained lymph vessels. Sentinel nodes are sent to the pathologist. Subsequently resection of the vulvar lesion is performed. When identification of the sentinel node is not successful because of low radioactivity, or by preference of the surgeon, the vulvar tumour is removed first. By resection of the vulvar tumour together with the primary Nano colloid injection sites the radiation background is greatly reduced, allowing easier identification of the sentinel nodes, especially when the primary tumour is near the groins. After removal of the sentinel nodes, the biopsy bed is re-examined for radioactivity, and if higher than 10% of the first excised lymph node, the dissection is continued in search of additional sentinel nodes.

5.1.4 Surgical protocol

Treatment consists of wide local excision of the vulvar tumour or a vulvectomy in combination with SLN procedure. All groins with a SLN on imaging should be explored; also when previously IFL was performed at that site. When sentinel nodes in one or two groins cannot be identified an inguinofemoral lymphadenectomy at either one or two sides should be performed, depending on the location of the tumour and consent of the patient. (Figures 2, 3 and 4) When preoperative imaging showed any enlarged groin node (shortest axis > 8 mm) this node should be removed.

5.1.5 Histopathology:

Macroscopy: the number of lymph nodes received should be described, as well as the size and macroscopic aspects of the lymph nodes. The lymph node should be cut in 2-3 mm slices, perpendicular to the long axis and then all slices should be embedded (do not embed different lymph nodes in the same block).

Microscopy: one routine H/E section (four mu) should be cut of all blocks and two unstained sections (do not cut deep into the block). If the sections are tumour negative step sections, 3 levels/mm (one section per 500 micro meter), should be cut. For the three sections at each level, one is stained with H/E, one is to be used for immunohistochemistry (cytokeratin AE1/AE3), while one spare section is preserved in case of technical difficulties with the IHC (include the first level for IHC). Metastases are defined as clusters of tumour cells of any size detected on haematoxylin and eosin slides or at immunohistochemistry, or isolated tumour cells detected at immunohistochemistry. Anucleate keratin-positive structures are not considered positive. The diameter of the sentinel node metastasis and presence of extranodal growth will be recorded.

Pathologic ultra-staging will only be performed on sentinel nodes and not on non-sentinel nodes as identified in full lymphadenectomy specimens.

Reporting: number of sentinel nodes. Number of lymph nodes in lymphadenectomy specimen. Number of nodes with metastatic involvement. Size of lymph node metastasis. Extra nodal tumour growth.

5.1.6 Additional surgery:

In case of a positive SLN on histology a full IFL is advised. However, local protocol might advise postoperative radiotherapy under certain circumstances.

5.1.7 Radiotherapy protocol

Standard (chemo) radiotherapy (see www.oncoline.nl for current standard treatment) is indicated postoperatively in case of more than 1 lymph node metastasis or in case of extracapsular tumour growth. Radiotherapy will include the inguinal and low pelvic lymph nodes. Radiotherapy should be initiated within 6 weeks after the final surgical procedure.

5.1.8 Follow-up

During the first 24 months follow-up will be done three-monthly: with physical examination including inspection and palpation of the groins and of the vulva, inspection of the legs (lymph oedema) and notification of the number of erysipelas episodes.

At months 6, and 12, and in case of suspected groin nodes, an ultrasound scan of the groins is requested. When ultrasonography shows enlarged or suspect lymph nodes, a FNA will be performed.

After 24 months the follow-up will be done in accordance with local protocols.

5.2 Use of co-intervention

Not applicable.

5.3 Escape medication

Not applicable.

6. INVESTIGATIONAL PRODUCT

Not applicable.

6.1 Name and description of investigational product(s)

Not applicable.

6.2 Summary of findings from non-clinical studies

Not applicable.

6.3 Summary of findings from clinical studies

Not applicable.

6.4 Summary of known and potential risks and benefits

Not applicable.

6.5 Description and justification of route of administration and dosage

Not applicable.

6.6 Dosages, dosage modifications and method of administration

Not applicable.

6.7 Preparation and labelling of Investigational Medicinal Product

Not applicable.

6.8 Drug accountability

Not applicable.

7. NON-INVESTIGATIONAL PRODUCT

Not applicable.

7.1 Name and description of investigational product(s)

Not applicable.

7.2 Summary of findings from non-clinical studies

Not applicable.

7.3 Summary of findings from clinical studies

Not applicable.

7.4 Summary of known and potential risks and benefits

Not applicable.

7.5 Description and justification of route of administration and dosage

Not applicable.

7.6 Dosages, dosage modifications and method of administration

Not applicable.

7.7 Preparation and labelling of Investigational Medicinal Product

Not applicable.

7.8 Drug accountability

Not applicable.

8. METHODS

8.1 Study parameters/endpoints

8.1.1 Main study parameter/endpoint

The main study endpoint is the number of women who develop a groin recurrence within 24 months after a negative SLN procedure in 1st recurrent vulvar cancer. Clinical examination is done every 3 months, with an USS of the groin at 6 and 12 months. In case of suspicious findings FNA or histologic biopsy is performed.

8.1.2 Secondary study parameters/endpoints

Feasibility of the SLN procedure in recurrent vulvar cancer

This is the success rate of detection and retrieval of the sentinel node, both related to the percentage of women, as well as groins in whom the proposed SLN surgery is successfully performed.

Perioperative and postoperative morbidity and mortality

Data collection at 6 weeks after every surgery by the physician. Type of surgery (SLN right groin, SLN left groin, IFL right, IFL left, vulva surgery, reconstructive surgery). Location of SLN found (within IFL region or not), surgical challenges (unintended lesion of vena saphena magna, bleeding, others), duration of surgical procedure, complications (wound infections, wound breakdown, lymph oedema (see adverse effect Appendix 1)), length of hospital stay, re-surgery, readmission.

Incidence of tumour positive sentinel nodes

All specimen will be examined according to the protocol (See section 5.1.) depth of tumour infiltration, presence of LVSI, number of SLN's per groin, number of removed nodes per groin.

Adjuvant treatment

Adjuvant groin treatment; IFL, and or radiotherapy.

8.1.3 Other study parameters

Baseline data:

FIRST procedure: age at first procedure, localisation of tumour (medial / lateral), tumour size, depth of infiltration, LVSI, number of SLN right groin, number of SLN

left groin, IFL right site (number of lymph nodes), IFL left site (number of lymph nodes), previous radiotherapy, presence of LS or dysplasia, previous reconstructive surgery.

Interval between first surgical treatment and moment of relapse, guessed / estimated distance (cm) between original tumour and relapse, localisation of relapsed tumour, tumour size.

Intention to remove SLN ipsi- or bilateral, agreement on performing IFL in case SLN is not detected or retrieved.

Questionnaires

EQ-5D-5L. Standardized descriptive system of health-related quality of life states consisting of five dimensions (mobility, self-care, usual activities, pain/discomfort, anxiety/depression) each of which can take one of five responses. The responses record five levels of severity (no problems/some problems/ moderate problems/severe problems/extreme problems) within a particular EQ-5D dimension. Besides the descriptive system, a standard vertical 20 cm visual analogue scale (similar to a thermometer) for recording an individual's rating for their current health-related quality of life state is part of the EQ-5D. It was developed by the EuroQol Group. (14, 15)

Decisional Conflict Scale (DCS). This scale measures: 1) health-care consumers' uncertainty in making a health-related decision; 2) the factors contributing to the uncertainty; and 3) health-care consumers' perceived effective decision making. Internal consistency coefficients range from 0.78 to 0.92. (16) This questionnaire will only be used at baseline.

Decision Regret Scale (DRS). The DRS is a 5-item scale and a useful indicator of health care decision regret at a given point in time. Internal consistency is good (Cronbach's alpha = 0.81 to 0.92). This questionnaire will be used to evaluate patient's decision 1 year after surgery. (17)

GCLQ7 questionnaire: This is a short version of the Gynaecologic Cancer Lymphedema Questionnaire. This questionnaire will be used at baseline, 6 and 12 months. (18)

8.2 Randomisation, blinding and treatment allocation

Not applicable.

8.3 Study procedures

Study Settings:

This study will be done within the existing partnership of the GROningen INternational Study on Sentinel nodes in Vulvar cancer (GROINSS-V) in hospitals that perform at least 20 SLNs yearly, and with experience of at least 5 SLN procedures in patients with recurrent V-SCC. In the first phase only the members of the writing committee will participate, all of them having experience with repeat SLN.(11) After 40 procedures other centres within the GROINSS-V consortium with similar experience can participate.

Preoperative dissemination:

Preoperative dissemination is performed by chest, abdominal and groin CT scanning. Ultrasound scanning of the groins is done, with fine needle aspiration of suspicious or enlarged nodes to rule out lymph node metastases.

For details on the *surgical procedure* see 5.1.3.

Questionnaires:

Questionnaires will be sent by the datacentre in Rotterdam, at baseline, 6 and 12 months, using e-mail with a link to web-based questionnaires. Sending and receiving questionnaires will be coordinated by a research nurse of the Erasmus MC. The participant should complete the web-based questionnaires by herself. The average time to complete questionnaires is approximately 15 – 30 minutes.

Participants are asked to complete questionnaires as much as possible at the indicated time points, but no more than one month sooner or later. In case participants are not able to receive or fill out web-based questionnaires, a paper version of the questionnaires will be sent with an answering envelop by the research nurse from the datacentre in Rotterdam. However, the use of web-based questionnaires is highly preferred.

Follow up:

Routine 3-monthly clinical examination is combined with ultra-sonographic assessment of the groins at 6 and 12 months in women treated with the SLN procedure.

8.4 Withdrawal of individual subjects

Subjects can leave the study at any time for any reason if they wish to do so without any consequences. The investigator can decide to withdraw a subject from the study for urgent medical reasons.

8.4.1 Specific criteria for withdrawal

Not applicable.

8.5 Replacement of individual subjects after withdrawal

Not applicable.

8.6 Follow-up of subjects withdrawn from treatment

Not applicable.

8.7 Premature termination of the study

The study will be terminated when the stopping rule is activated because of too many groin recurrences. See 4.4. sample size calculation for the stopping rules.

9. SAFETY REPORTING

9.1 Temporary halt for reasons of subject safety

In accordance to section 10, subsection 4, of the WMO, the sponsor will suspend the study if there is sufficient ground that continuation of the study will jeopardise subject health or safety. The sponsor will notify the accredited METC without undue delay of a temporary halt including the reason for such an action. The study will be suspended pending a further positive decision by the accredited METC. The investigator will take care that all subjects are kept informed.

9.2 AEs, SAEs and SUSARs

9.2.1 Adverse events (AEs)

Adverse events are defined as any undesirable experience occurring to a subject during the study, whether or not considered related to treatment. We will not report any adverse events.

9.2.2 Serious adverse events (SAEs)

A serious adverse event is any untoward medical occurrence or effect that:

- results in death;
- is life threatening (at the time of the event);
- requires hospitalisation or prolongation of existing inpatients' hospitalisation;
- results in persistent or significant disability or incapacity;
- is a congenital anomaly or birth defect; or
- any other important medical event that did not result in any of the outcomes listed above due to medical or surgical intervention but could have been based upon appropriate judgement by the investigator.

An elective hospital admission will not be considered as a serious adverse event.

The investigator will report death, life threatening events (at the time of the event) and the occurrence of groin recurrence to the sponsor without undue delay after obtaining knowledge of the events. The following SAEs: prolonged admittance or re-admittance to the hospital with problems like wound breakdown, urinary tract infections, wound infections, and erysipelas will only be reported at the end of the study, not in any annual safety report or otherwise since all are regular SAEs, related to the treatment and not related to the study.

The sponsor will report the SAEs death, life threatening events (at the time of the event) and the occurrence of groin recurrence through the web portal ToetsingOnline to the accredited METC that approved the protocol, within 7 days of first knowledge for SAEs that result in death or are life threatening or occurrence of a groin recurrence, followed by a period of maximum of 8 days to complete the initial preliminary report. All other SAEs will not be reported.

9.2.3 Suspected unexpected serious adverse reactions (SUSARs)

Not applicable.

9.3 Annual safety report

Groin recurrences and death of disease will be closely monitored. Safety reviews will be presented confidentially to the principal investigators every year. These annual reviews will include data on SAEs, number of deaths and cause of death, and number of groin recurrences. When the upper boundary of the stopping rule is passed all principal investigators will be informed immediately, and patient recruitment will instantaneously be paused. After interim safety analyses by the Safety Committee (see below) the study will be stopped, or continued, with or without adaptations.

9.4 Follow-up of adverse events

All AEs will be followed until they have abated, or until a stable situation has been reached. Depending on the event, follow up may require additional tests or medical procedures as indicated, and/or referral to the general physician or a medical specialist.

SAEs need to be reported till end of study within the Netherlands, as defined in the protocol.

9.5 Safety Committee

An independent Safety Committee will be appointed in case the stopping rule is activated to decide to definitively stop, or continue the study.

The Safety Committee will consist of an independent gynaecologic oncologist, an oncologic surgeon, an epidemiologist, (all three with experience in clinical trials and not entering patients in the study), a lay-person representing patients, and an independent biostatistician.

10. STATISTICAL ANALYSIS

Baseline data will be presented in a descriptive manner. Frequencies, relative frequencies, means and standard deviations will be calculated. To test for differences in baseline data, the Chi square and analysis for variance (ANOVA) are used for categorical and continuous variables respectively.

Statistical tests will be done two-sided and p-values are considered statistically significant when $p < 0.05$. Statistical analyses will be carried out using the statistical package SPSS for Windows (SPSS, Chicago, IL, USA).

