4.4 Sample size calculation

Approximately 18% of women will have groin metastases at the moment of their first vulvar cancer recurrence. Of these, approximately 20% will be detected prior to surgery (based on imaging and FNA) and these women will not be offered a SLN procedure, but advised to undergo an IFL(s). They will be asked for the observational arm of the non SLN cohort. (See figure 2)

The remaining patients will be informed about the study, they can decide on standard IFL (group A) or refuse any surgery of the groin(s) (group C) In 75% of cases that undergo SLN (group B) it will be possible to retrieve the SLN. In approximately 14,5% of women undergoing a SLN procedure a tumour positive node will be present. It is not expected that the change of a successful SLN procedure relates to the presence or absence of a positive groin node. We expect to find a positive SLN in 11% of cases undergoing a SLN procedure, a negative SLN in 64%, and an unsuccessful procedure in 25%. This corresponds to respectively 10.5%, 61.8% and 24.1% of all included patients.

Percentage failure of SLN or IFL is known for neither procedure in the recurrent setting. In the primary setting groin recurrence after negative IFL and after negative SLN are both about 3%.

Sample size for V2SLN is calculated based on a conservatively estimated groin recurrence rate of 3%, with a maximum additional groin failure rate of SLN in local recurrent vulvar SCC of 5%. The sample size, considering an alpha of 0.10 and a beta of 0.20, is then calculated to be 150 patients with a first vulvar cancer recurrence undergoing a SLN procedure (group B) and a negative SLN (Figure 2) So, we expect that approximately 243 women with a 1st recurrence of vulvar cancer should be included in the study. Stopping rules with dynamic boundaries were constructed to guarantee the safety of the study by continuously monitoring the number of groin recurrences. See Appendix 1 for a detailed description of these stopping rules.

[figure not shown]

Figure 2 Flow diagram of calculation of sample size

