Appendix 1: Stopping rules

The predictive probability design for phase II cancer clinical trial as described by Lee and Liu was used to develop the stopping rule for this study. (20) This method has the advantage over two and three stage designs that the safety can be monitored constantly rather than at a pre-specified fixed number of patients.

Under the hypothesis testing framework, this clinical trial is designed to test

$$H_0 : p \leq p_0$$

against

$$H_1 : p \geq p_1$$

where p represents the success rate of the SLN procedure, so that $1 - p$ is the failure rate. p_1 is the target success rate and p_0 is the minimally acceptable success rate. We consider a failure rate of SLN of 8% (i.e. $1 - p_1$) to be maximally acceptable, and our target failure rate (i.e. $1 - p_0$) is 3%. The study is designed such that $P(\text{Accept New Treatment}|H_0) \leq \alpha$, and $P(\text{Reject New Treatment}|H_1) \leq \beta$, where the maximum type I error α and the maximum type II error rate β are both set to 0.10.

In this model, we calculate PP continuously after 10 patients (i.e., with cohort size of 1) to monitor the treatment safety.

The stopping rule is based on the predictive probability (PP) of concluding a positive result by the end of the trial based on the cumulative information in the current stage. In this model, we calculate PP continuously after 10 patients (i.e., with cohort size of 1) to monitor the treatment safety. The trial is stopped when the PP drops below the lower bound ϑ_l , where ϑ_l is a parameter that is optimized by the method. The method of Lee and Liu also includes an option for early stopping of the trial in case the PP is very close to 1, using an upper bound ϑ_u . However, we did not utilize this option, since we do not expect to have to stop the trial in case the SLN procedure has a lower groin failure rate than IFL.

In the Bayesian predictive probability approach, we assume that the failure rate ($1 - p$) has a prior distribution of Beta (0.2; 0.8), which has a prior mean of 20%. Using the software of Lee and Liu (see

<https://biostatistics.mdanderson.org/SoftwareDownload/SingleSoftware/Index/84>) we calculated the minimum number of patients to obtain sufficient power with acceptable type I error rate using a 'max power' approach. The results gave a sample size of 150 patients, with

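### The error rates behind the 150 women are stated inconsistently (Section 4.4, Section 10, Appendix 1), and the 8% and 3% labels in Appendix 1 are swapped

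*Protocol*

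**What the plan says.** - **Section 4.4** assumes a 3% groin recurrence rate with at most 5 points added, so 8%. It then says "The sample size, considering an alpha of 0.10 and a beta of 0.20, is then calculated to be 150 patients" with a negative SLN. It does not say whether alpha is one-sided or two-sided, and it refers to Appendix 1 for the stopping rules.
- **Appendix 1** sets one-directional hypotheses on the success rate p, "where the maximum type I error α and the maximum type II error rate β are both set to 0.10". The program input agrees: type I error 0.10, power 0.90, p0 = 0.92, p1 = 0.97, Nmax 150.
- **Appendix 1** defines the parameters as "p_1 is the target success rate and p_0 is the minimally acceptable success rate". The next sentence, starting "We consider a failure rate of SLN of 8" percent, equates that upper limit with 1 − p1 and the 3% target with 1 − p0, which is the reverse.
- **Section 10**, straight after the baseline comparisons, says "Statistical tests will be done two-sided and p-values are considered statistically significant when" p < 0.05. No endpoint is exempted.
- **Section 10.1** gives the primary endpoint as a percentage. It names no test, level or acceptance criterion and does not mention Appendix 1. Its denominator is women with a successful SLN procedure.
- **Section 12.5** ends the study when 125 successfully treated patients have two years of follow-up.

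**The concern.** This is a single-arm safety study with one main decision: whether the recurrence rate after a negative SLN is low enough to replace IFL. The decision needs one criterion, fixed before the count is known. The chapter that should state it contains only a general two-sided 5% sentence. The criterion that produced the sample size is in an appendix to which 10.1 does not point, and Section 4.4 gives a different beta for the same 150. Someone writing the final analysis could defend more than one level after seeing the number of recurrences. Taken literally, the swapped labels would also make the null p ≤ 0.97 and the alternative p ≥ 0.92, which overlap and cannot be tested against each other.

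**Working it through.** **Inputs.** N = 150; p0 = 0.92 (8% failure) and p1 = 0.97 (3% failure) from the program input; stopping boundaries from the Appendix 1 output; alpha and beta from 4.4, Section 10 and Appendix 1.

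**1. The plan's own figures.** At 150 patients the output is negative at 142 or fewer successes, so positive at 7 or fewer recurrences. An exact binomial recursion through the printed boundaries (n = 10 to 150, one patient at a time) gives:

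| Quantity | Printed | Recomputed |
|---|---|---|
| Alpha | 0.0805 | 0.0805 |
| Power | 0.9160 | 0.9160 |
| E(N) at p0 | 93.4786 | 93.4786 |
| E(N) at p1 | 147.7381 | 147.7381 |

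So 150 with a cut-off of 7 is a one-sided design with alpha and beta both capped at 0.10, run with the correct assignment of 8% and 3%.

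**2. Section 10 applied to the primary endpoint.** Let X be the number of recurrences among 150. The tail against 8% is P(X ≤ k) with X ~ Bin(150, 0.08). The exact upper 97.5% limit is the 0.975 quantile of Beta(k + 1, 150 − k). The power of a cut-off k is P(X ≤ k) with X ~ Bin(150, 0.03), here without interim stopping.

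| k | Tail at 8% | Upper 97.5% limit | Power at 3% |
|---|---|---|---|
| 5 | 0.0169 | 7.61% | 0.704 |
| 6 | 0.0397 | 8.50% | 0.834 |
| 7 | 0.0806 | 9.38% | 0.917 |
| 8 | 0.1442 | 10.24% | 0.962 |

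One-sided 0.10 is met up to k = 7. Two-sided 0.05 needs a tail of at most 0.025, so k ≤ 5. The readings differ at 6 and 7. At a true 3%, the chance of exactly 6 or 7 is 0.917 − 0.704 = 0.21.

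**3. Section 4.4 as stated.** Normal approximation: n = [(z(1−α)·√(0.08·0.92) + z(1−β)·√(0.03·0.97)) / 0.05]².
- One-sided 0.10, beta 0.20: [(1.2816·0.2713 + 0.8416·0.1706) / 0.05]² ≈ 96.5, so 97. The first exact n is 98 (cut-off 4), and every n from 114 works.
- Two-sided 0.10 (0.05 per tail), beta 0.20: about 139.1, so 140. The first exact n is 129, and every n from 162 works. N = 150 with cut-off 6 also works (tail 0.0397, power 0.834).

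**4. The 125 patients in Section 12.5.** With X ~ Bin(125, 0.08): P(X ≤ 5) = 0.059, P(X ≤ 6) = 0.120, P(X ≤ 7) = 0.209. At 125, neither 6 nor 7 recurrences meets alpha 0.10.

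**5. The denominator in 10.1.** Section 4.4 expects 64% negative, 11% positive and 25% unsuccessful procedures. Then 150 SLN-negative women correspond to 150 × 75/64 ≈ 176 successful procedures. Seven recurrences are 7/150 = 4.7% on one denominator and 7/176 = 4.0% on the other.

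**The case against.** The strongest objection is that Appendix 1 plainly governs the primary question. It is the only place with hypotheses for it, it states error rates and prints an acceptance region, and 4.4 refers to it. The Section 10 sentence is general text after the baseline tests, and 10.1 plans no p-value. On that reading two-sided 0.05 belongs to the comparisons in 10.2 and 10.3, and nothing conflicts for the primary endpoint. This largely stands. It is the more natural reading, but nothing in the text secures it: the sentence exempts nothing and 10.1 does not point to Appendix 1.

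Three stronger conclusions that a reader might draw are not supported:
- *That all the discrepancies change the verdict at 6 or 7 recurrences.* Only the Section 10 sentence, if applied, puts both counts in doubt; a two-sided reading of the 0.10 in 4.4 would affect 7 alone. The difference in beta bears on the justification of N, not on the verdict at a given count.
- *That 4.4 should have given 98, not 150.* That assumes a one-sided alpha, which 4.4 does not state. With 0.10 two-sided, 150 meets beta 0.20.
- *That the swapped labels spoil the stopping rule.* The program used the correct assignment, so every printed boundary stands.

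**Conclusion.** The inconsistencies are real, and they are errors of statement, not of calculation. Appendix 1's design reproduces exactly as one-sided alpha 0.10 and beta 0.10. Section 4.4 misreports its beta as 0.20, and the 8% and 3% labels are reversed.

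The effect on the decision is conditional. If the Section 10 sentence were applied to the primary endpoint, the largest acceptable count would fall from 7 to 5 of 150, and power at a true 3% from 0.916 to 0.70. If it covers only the other comparisons, the criterion is unchanged and merely missing from where it is needed. For the beta in 4.4, a one-sided alpha would imply roughly 98 to 114 women; since sidedness is not stated, the firm point is only that 4.4 and Appendix 1 give different betas for the same 150.

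These figures assume exact binomial inference, 150 evaluable SLN-negative women, and 8% and 3% as the unacceptable and target failure rates.

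**What to change.** - **Section 4.4:** state one-sided alpha 0.10 and beta 0.10 (attained alpha 0.0805, power 0.916).
- **Appendix 1:** write 8% = 1 − p0 and 3% = 1 − p1.
- **Sections 10 and 10.1:** state that the primary conclusion follows the one-sided Appendix 1 rule, positive at 7 or fewer recurrences among 150 evaluable SLN-negative women. Limit two-sided p < 0.05 to the other comparisons.
- **Section 12.5:** in the same amendment, reconcile the 125 patients with the 150. A cut-off of 7 cannot be carried over to 125; there the largest count meeting alpha 0.10 is 5 (tail 0.059, power 0.826 at 3%).
- **Section 10.1 denominator:** reconcile women with a successful procedure with SLN-negative women, so that the reported percentage and the decision rule use the same group.

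The first three changes are wording only and leave the boundaries and the 150 as computed. The last two need a decision by the sponsor on the number and the group. If 150 SLN-negative women is confirmed, they too are wording changes.
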